15.0 Transfer of data

Patient data will be transferred between sites via the EMBARC database hosted by HIC.

16.0 Study management and oversight arrangements

16.1 Study management group

The study will be co-ordinated by a Study Management Group (SMG), consisting of the grant holder Chief Investigator ([name]), study lead ([name]) external Principal Investigators (PIs), study manager and research nurse or equivalent.

16.2 Study steering committee

A Study Steering Committee will be established to oversee the conduct and progress of the study. The terms of reference of the steering committee are detailed in the study management file. Minutes of the steering committee will be maintained in the study management file.

16.3 Data monitoring committee

An independent data monitoring committee will be established to oversee study progress. The terms of reference of the data monitoring committee are detailed in the study management file. Minutes of the data monitoring committee will be maintained in the study management file.

16.4 Inspection of records

The CI, PIs and all institutions involved in the study will permit study related monitoring, audits, and research ethics committee review. The CI agrees to allow the Sponsor or, representatives of the Sponsor, direct access to all study records and source documentation.

16.5 Funding

Funding is provided by Asthma and Lung UK, The European Respiratory Society and by additional sponsors including the European Union Innovative Medicines Initiative and pharmaceutical companies. Investigators will not receive any financial incentive for recruitment or participation in this study over and above their normal conditions of employment.

17.0 Good clinical practice

17.1 Ethical conduct of the study

The study will be conducted in accordance with the principles of Good Clinical Practice (GCP). In addition to Sponsorship approval, a favorable ethical opinion will be obtained from an appropriate REC. Authorisation from an appropriate competent

authority(s) and appropriate NHS R&D permissions(s) will be obtained prior to commencement of the study.

18.0 Confidentiality and 19.0 Data Protection

The CI and trial staff will comply with all applicable medical confidentiality and data protection principles and laws with regard to the collection, storage, processing and disclosure of personal data.

The CI and study staff will also adhere to the NHS Scotland Code of Practice on Protecting Participant Confidentiality or equivalent.

All study records and personal data will be managed in a manner designed to maintain participant confidentiality. All records, electronic or paper, will be kept in a secure storage area with access limited to appropriate study staff only. Computers used to collate personal data will have limited access measures via user names and passwords.

Personal data concerning health will not be released except as necessary for research purposes including monitoring and auditing by the Sponsor, its designee or regulatory authorities providing that suitable and specific measures to safeguard the rights and interests of participants are in place.

The CI and study staff will not disclose or use for any purpose other than performance of the study, any personal data, record, or other unpublished, confidential information disclosed by those individuals for the purpose of the study. Prior written agreement from the Sponsor will be required for the disclosure of any said confidential information to other parties.

Access to collated personal data relating to participants will be restricted to the CI and appropriate delegated trial staff.

Where personal data requires to be transferred, an appropriate Data Transfer Agreement will be put in place.

Published results will not contain any personal data that could allow identification of individual participants.

20.0 Insurance and Indemnity

The University of Dundee and Tayside Health Board are co-sponsoring the study.

20.1 Insurance

The University of Dundee holds Clinical Trials indemnity cover which covers the University's legal liability for harm caused to patients/participants.

Tayside Health Board will maintain its membership of the Clinical Negligence and Other Risks Insurance Scheme ("CNORIS") which covers the legal liability of Tayside in relation to the study.

Where the study involves University of Dundee staff undertaking clinical research on NHS patients, such staff will hold honorary contracts with Tayside Health Board which means they will have cover under Tayside's membership of the CNORIS scheme.

20.2 Indemnity

The sponsors do not provide study participants with indemnity in relation to participation in the Study but have insurance for legal liability as described above.

21.0 Adverse events

21.1 Definitions

Adverse Event (AE)	Any untoward medical occurrence in a clinical research participant which does not necessarily have a causal relationship with study participation	
Serious Adverse Event (SAE)	 A serious adverse event is any untoward medical occurrence that: results in death is life threatening requires hospitalisation or prolongation of existing hospitalisation results in persistent or significant disability or incapacity is a congenital anomaly or birth defect Or is otherwise considered serious 	

21.2 Recording and reporting adverse events

Participants will be asked about any adverse events related to study procedures at the visit. We will not record all AE's and SAE's that occur to study participants; instead only those events that occur **at the study visit** and which are directly the result of study procedures. This would include adverse events related to venepuncture (*for e.g. bruising, swelling, bleeding from the site, light headedness and rarely, infection at the site that blood has been taken from*) for research purposes. These risks will be clearly

stated in the Patient Information Sheet. All AEs and SAEs will be recorded on the AE Log in the CRF and will be assessed for severity by the CI or delegate.

The CI/PI will make a clinical judgment as to whether an AE is of sufficient severity to require the participant's removal from the study. A participant may also voluntarily withdraw from treatment due to what he or she perceives as an intolerable AE. If either of these occurs, the participant should, if required, be offered an end of study assessment and be given appropriate care under medical supervision until symptoms cease, or the condition becomes stable.

The CI or delegate will ask about the occurrence of AEs and SAEs and hospitalisations at every visit during the study. SAEs which are both unexpected and related to study participation will be reported to the Sponsor Team and CI in the first instance and then REC as appropriate in accordance with current advice from the Health Research Authority (HRA) regarding safety reporting for Non-CTIMP studies. Non- UK sites will also follow their own countries regulations on safety reporting.

Worsening of the condition under study will not be classed as an AE but will be defined as an outcome. Pre-specified outcome(s) will not be classed as an AE but as an outcome. Elective admissions and hospitalisations for treatment planned prior, where appropriate, will not be considered as an AE.

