10.0 Safety assessments

Participants will be asked about adverse events at all visits. We will record adverse events that occur to study participants during a study visit. If any serious adverse events (SAEs) occur they will be reported to the Sponsor based at Ninewells Hospital, Dundee in a timely manner. Refer to section 21.2 for full details on reporting.

The major predictable adverse effects in the study are as follows:

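### The adverse event recording rule in section 21.2 requires onset at the study visit, which conflicts with a delayed harm it lists as included, and section 10.0 sets a different scope

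*Protocol*

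**What the plan says.** Protocol section 21.2 sets two joint conditions for recording. The first is timing: "We will not record all AE's and SAE's that occur to study participants; instead only those events that occur" at the study visit (the protocol emphasises these words). The second is cause: "and which are directly the result of study procedures". The next sentence gives venepuncture harms as events that this would include: "bruising, swelling, bleeding from the site, light headedness and rarely, infection at the site that blood has been taken from".

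Three further sentences in section 21.2 bear on scope:

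- Recording: "All AEs and SAEs will be recorded on the AE Log in the CRF and will be assessed for severity by the CI or delegate".
- Asking: "The CI or delegate will ask about the occurrence of AEs and SAEs and hospitalisations at every visit during the study".
- Reporting: "SAEs which are both unexpected and related to study participation will be reported to the Sponsor Team and CI in the first instance", and then to the ethics committee as appropriate. No visit condition is attached.

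Section 10.0 is the earlier summary. It records adverse events that happen during a study visit, without asking whether a procedure caused them. On serious events it says "If any serious adverse events (SAEs) occur they will be reported to the Sponsor", with no limit by cause, expectedness or timing. It then refers to section 21.2 for the details of reporting.

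**The concern.** Restricting recording to procedure-related events is a reasonable choice for an observational cohort with no study treatment, and is not questioned here. The difficulty is the added timing condition. Some harms of blood sampling show themselves only later, and the protocol's own list contains one. A site that follows the emphasised words will leave such an event off the log; a site that follows the example will enter it.

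The study is multi-centre and international, with sampling planned at months 0, 12, 24 and 36 and at optional exacerbation visits. If sites apply different sentences, their logs will not be comparable, and the record of what the procedures do to participants will be incomplete. Sites also need to know which serious events go to the Sponsor, and sections 10.0 and 21.2 give different answers.

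**Working it through.** No arithmetic applies: the protocol gives no adverse event rate, and no planned analysis uses these data. The check is to take types of event and read each rule as written.

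| Event | Recorded under 21.2 rule | Reported under 21.2 | Under 10.0 |
|---|---|---|---|
| (a) Non-serious venepuncture-site infection appearing after the visit | No by the timing condition; yes by the example list | Not applicable | Not recorded |
| (b) Related, unexpected SAE starting after the visit | No | Yes | Reported |
| (c) Related, expected SAE starting after the visit | No | No | Reported |
| (d) Unrelated SAE | No | No | Reported |
| (e) Non-serious AE during a visit, not caused by a procedure | No | Not applicable | Recorded |

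Row (a) is the contradiction inside section 21.2. The condition and the example stand in consecutive sentences and cannot both be applied to an infection that appears later. Bruising and swelling can also appear later; light-headedness and bleeding can occur at the visit and raise no difficulty.

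Row (b) is a mismatch between recording and reporting. Section 21.1 counts hospitalisation as serious, and an admission will often begin after the participant has left. Such an event, if related and unexpected, must be reported, yet the recording rule gives it no place on the AE Log.

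Row (c) is the serious category that section 21.2, read literally, neither records nor reports.

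Rows (d) and (e) are differences of scope between the two sections. Row (d) is narrowed because section 21.2 does not class worsening of bronchiectasis, or planned admissions, as adverse events.

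The every-visit question does not by itself resolve row (a). It brings out events since the last visit, but the timing condition, read literally, still keeps them off the log. It may also come late. The first follow-up is at month 12 with a window of 3 months either side, so 12 - 3 = 9 to 12 + 3 = 15 months after the first sampling, unless there is an exacerbation visit sooner. Section 1.4 says only that participants attend at least once, so for some the question may never come.

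**The case against.** The best case for the protocol has four parts.

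1. Section 10.0 is a summary that names section 21.2 as the place for reporting details, so a site can tell which section governs. This largely stands. It reduces the difference between the sections to something to be tidied, although section 21.2 narrows which serious events are reported rather than only explaining how.

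2. The sentence that all AEs and SAEs go on the log comes shortly after the scope rule and is most naturally read as all events within that scope. This stands as a fair reading. A reader might infer that section 21.2 flatly contradicts itself by first refusing and then requiring complete recording; the text does not force that conclusion. It should still say what it means.

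3. Delayed harm is not simply lost. Unexpected related serious events are reportable whenever they start, participants are asked at every visit, and site infection is expressly listed. This stands against any claim that every delayed event disappears by rule. What remains exposed is the AE Log entry for delayed non-serious events and for delayed serious events that are related.

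4. Only site infection comes from the protocol's own list. A reader might extend the point to late nosebleeds after nasal brushing or bronchospasm after leaving the clinic. Sections 10.1 and 10.2 name bronchospasm and nosebleeds as predictable effects but do not describe a delayed form, so these cases follow from the rule's logic rather than from anything the protocol states.

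None of this removes row (a): the timing condition and the site-infection example remain incompatible.

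**Conclusion.** The point holds in a limited form. Read literally, the timing condition in section 21.2 keeps off the AE Log the delayed procedure-related events that its example shows it means to capture, and sections 10.0 and 21.2 differ on relatedness and on which serious events are reported. This assumes that venepuncture-site infection would normally become apparent after the visit and that sites apply the emphasised condition as written.

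No numerical size can be given. It is tempting to multiply 2500 participants by four scheduled visits and by some rate of delayed events. The protocol gives no such rate, promises attendance only at least once, and calls its recruitment numbers indicative. That product would also count as lost the unexpected related serious events that remain reportable.

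The endotyping objectives, the sample size and the proposed analyses are unaffected. This is a worthwhile correction to safety wording, not a defect that must be cured before the study can be relied on.

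**What to change.** Use one scope in both sections:

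- Remove the condition that the event occurs at the study visit from section 21.2, and the matching during-visit limit from section 10.0.
- State in both that any AE or SAE judged related to a study procedure is recorded, whenever it starts. Cover events since the last procedure that are brought out by the existing every-visit question, and events that participants report between or after visits.
- State that the sentence on entering all AEs and SAEs in the log means all events within that scope.
- Reconcile the SAE reporting sentence in section 10.0 with section 21.2, so that the same serious events are reportable under both.

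The cost is a wording amendment and a few more log entries. Participants are already asked at every visit, so no new assessment is needed.

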22.0 Protocol amendments deviations and breaches

The chief investigator will seek approval for any amendments to the protocol or other study documents from the Sponsor, REC and NHS R&D Office(s). Amendments to the protocol or other study docs will not be implemented without these approvals.

In the event that the CI needs to deviate from the protocol, the nature of and reasons for the deviation will be recorded in the CRF, documented and submitted to the Sponsor. If this necessitates a subsequent protocol amendment, this will be submitted to the Sponsor for approval and then to the appropriate REC and lead NHS R&D Office for review and approval.

In the event that a serious breach of GCP or protocol is suspected, this will be reported to the Sponsor Governance office immediately.

23.0 Feedback of results and Incidental findings

In the majority of cases we do not anticipate that results of the tests performed will immediately influence management. Any incidental findings (e.g. previously undiagnosed condition) considered to be clinically significant will be reported to the

participant's GP and/or consultant by the CI or Site PI, with the consent of the participant. The patient's GP will be informed of their participation in this study. Two examples of where relevant clinical information could be found would be new diagnosis of alpha-1 antitrypsin deficiency, as the study will measure alpha-1 antitrypsin and diagnosis of primary ciliary dyskinesia through assessment of cilia function and structure. If these diagnoses are made they will be communicated to the physician at the site who should make appropriate arrangements for management and follow-up of the patient.

24.0 Study Record retention

All study documentation, results and data will be archived in compliance with Sponsor Standard Operating Procedures. All trial documentation, electronic and paper, will be kept for 10 years. Medical records will be maintained in compliance with local NHS policy on retention of medical records. The CI will be responsible for arranging the archiving of the TMF and ensuring that research data is archived in a way that will permit accurate reconstruction of the research. Sites will be responsible for archiving local trial records including the ISF. Sponsor will be responsible for archiving the Sponsor file.

25.0 End of Study

The end of the study is defined as the last patient last visit. The Sponsor or Chief Investigator have the right at any time to terminate the study for clinical or administrative reasons.

The end of the study will be reported to the Sponsor and REC within 90 days or 15 days if the study is terminated prematurely. The CI will ensure that any appropriate follow up is arranged for all participants.

A summary report of the study will be provided to the Sponsor and REC within 1 year of the end of the study.

26.0 Reporting, publications and notification of results

26.1 Authorship policy

Ownership of the data arising from this study resides with the study team and their respective employers. On completion of the study, the study data will be analysed and a clinical study report will be prepared.

Authorship on publications shall be determined in accordance with ICMJE recommendations.

26.2 Publication

The clinical study report will be used for publication and presentation at scientific meetings. Summaries of results will also be made available to Investigators for dissemination within their clinical areas (where appropriate and according to their discretion).

